## **14. Plan and rationale for controlling the type I error (multiplicity of tests)**

We will not consider the inflation of the type I error.

## **15. Sub-group analyses**

Because hs-cTnI increases during the first hours post-chest pain, its value may be more informative after few hours. Therefore, we plan a subgroup analysis in patients with less than three hours between chest pain onset and hs-cTnI measurement.

## **16. Description of baseline patient characteristics**

The baseline characteristics will be summarized for the full cohort and according to the main and second outcomes, respectively: presence NSTEMI versus no NSTEMI and presence of MACE at 30 days versus no MACE at 30 days. The baseline is the time of the patient assessment by the HEMS.

The means, the standard deviations and the number of missing values will be presented for the following continuous variables:

- age (years)
- body mass index (kg/m^2)

The proportion of patients will be presented for the following categorial variables:

- Gender
- Risk factors of coronary artery disease (CAD):
  - HBP
  - Hypercholesterolemia
  - Diabetes mellitus
  - Family history of coronary artery disease
  - Active smoking
  - Past smoking (weaned > 5 years prior to recruitment)
- Cardiovascular history:

- Stented AMI
- Coronary by-pass
- Peripheral vascular disease
- Chronic kidney disease
- Stroke/ TIA
- Current medication:
  - ACE/ ARA2
  - Calcium inhibitors
  - Beta blockers
  - Anti platelet therapy
  - VKAs
  - Statins

We will also describe characteristics linked to the initial HEMS evaluation:

- Clinical presentation evocative of AMI on a 3-point scale (highly unlikely, moderately likely, highly likely)
- Delay between chest pain onset and HEMS evaluation ( $\leq 3$  hours versus  $> 3$  hours)
- HEMS ECG findings (normal, ST-segment depression, localized negative T-waves, left bundle branch block, other findings)

The frequency and percentage of patients in each category and the number of missing values will be reported for categorical variables: gender (male / female), risk factors (HBP, Hypercholesterolemia, Diabetes mellitus Family history of coronary artery disease, Active or past smoking), cardiovascular history and medication. For characteristics with multiple modalities, some may be merged in the case of small frequencies.

P-values will be reported with no correction for multiplicity. Categorical variables will be compared using a Chi-2 test (or Fisher exact test if the expected number of participants is less than 5), while continuous variables will be compared using a Student test (or Wilcoxon test if the minimum number of participants between the two groups is less than 30).

## 17. Description of the outcomes

NSTEMI and MACE at 30 days will be reported with the related frequency and proportion, knowing that a NSTEMI involve systematically a MACE at 30 days.

## 18. Description of the hs-cTnI discriminative capacities

The primary objective is to determine the pre-hospital capillary hs-cTnI threshold that maximizes the Youden index. The Euclidean distance (also called the upper-left index) will also be estimated. For the corresponding thresholds, the results will be reported on the related ROC curve. The related effectives (true positives and negatives, false positives and negatives) will be reported. The accuracy will also be computed (proportion of true results). On the same figure, the results related to the pre-hospital venous-based hs-cTnI will be reported. The difference between the two curves will be estimated and the corresponding bilateral test to evaluate the significance will be performed from the 95%CI (confidence interval).

The intra-class correlation coefficient (ICC) will additionally provide a single measure of the agreement between the capillary- and venous-based methods. Two scatter plots will be proposed to represent the degree of concordance: a plot with the pre-hospital venous-based hs-cTnI (y-axis) against the capillary-based measurements (x-axis), and a Bland–Altman plot with the difference between the two measurements (y-axis) against the average of the two measurements (x-axis).

The discriminative performance of the pre-hospital hs-cTnI will then be estimated for the MACE at 30 days as outcome. For that purpose, two ROC curves on the same graph will be plotted for the capillary- and venous-based measurements. The related AUCs and differences will be reported.

Depending on the results at this stage, the rest of the analyses will be performed according to the venous or the capillary method. In case of an equivalence, we will choose the capillary method because of its feasibility in a real-life setting.

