## 7. Objectives and related endpoints (units and calculations used to derive outcomes)

An adjudication committee oversees the validation of the events considered in the following objectives and outcomes.

The primary objective is to determine the thresholds of the pre-hospital capillary and venous hs-cTnI that maximizes the Youden J index. The event to predict is the non ST-elevation acute coronary syndrome at hospital discharge (NSTEMI). The sensitivity is the proportion of patients with an hs-cTnI level higher or equal to the threshold among the patients with the syndrome. The specificity is the proportion of patients with an hs-cTnI level lower than the threshold among the patients without the syndrome. We will also determine the ROC (receiver operating characteristic) curves and the related areas under the curve (AUC) related to the two methods.

**Figure 1.** Decision tree for ruling-out ruling-in the patients with a suspicious myocardial infarction after their emergency admission.

The secondary objectives of the VALIDATE project are to study the discriminative capacities of the pre-hospital hs-cTnI measured by two different testing methods (capillary and venous whole blood), and to select the method with the best performances. For that purpose, we aim:

- To evaluate the most relevant hs-cTnI measurement between the capillary- and the venous-based methods by i) reporting the concordance between the pre-hospital hs-cTnI measured by the capillary and venous methods, and ii) comparing the related AUCs for discriminating patients with NSTEMI.
- To estimate and compare the discriminative performances of the two methods by considering the Major Adverse Cardiac Events (MACE) occurrence at 30 days (ROC curves, AUCs, and Youden J index). Note that a NSTEMI systematically implies an outcome of MACE at 30 days.

Depending on the results at this stage, the rest of the analyses will be performed according to the venous or the capillary method, depending on their discriminative performances. In case of an equivalence, we will choose the capillary method because of its feasibility in a real-life setting. We will further investigate its usefulness to improve the ruling-in and ruling-out process described in Figure 1. More precisely, we aim:

- To propose a pre-hospital predictive tool of the probability of NSTEMI at hospital discharge. The candidate predictors will be the available demographic, clinical data, and pre-hospital hs-cTnI level.

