## **10. Sample size**

For the primary objective, we expect a sensitivity of 95%. We aim to include 73 patients for a maximum length of the 95% confidence interval equals 10% (+/-5%). Assuming a NSTEMI prevalence of 10%, 730 patients must be analyzed to achieve this precision. By anticipating a 10% rate of non-exploitable data (missing value, lost to follow-up, etc.), 800 inclusions are necessary.

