## **13. Level of statistical significance (p-values, confidence intervals, one- or two-sided)**

Statistical significances will be achieved for p-values lower the 5% by using two-sided alternative hypotheses and two-sided 95% confidence intervals. The 95%CI will be estimated by non-parametric bootstrap.

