## **19. Proposition and validation of a predictive tool for pre-hospital rule-out and rule-in**

The cohort will be divided into two parts: two thirds for learning and one third for validation. The description of the two samples will be performed with the same baseline variables listed in the section 16. No p-value will be computed because of the random allocation of the patients. Instead, standardized mean differences will be estimated to evaluate the comparability of the two samples.

From the learning sample, a logistic model will be estimated with LASSO penalization to select the subset of predictors among the following list of candidates: age, gender, body mass index, active smoking, stented heart disease, bypassed heart disease, compatible clinical history, delay after onset of pain lower than 3h; normal ECG evaluated by the HEMS, and the following risk factors: hypertension, diabetes, hypercholesterolemia, family history and hs-cTnI. The outcome will be the diagnosis of NSTEMI. We will perform a 20-fold deviance-based cross-validation to choose the best tuning parameter.

A particular attention will be paid to the interaction between hs-cTnI and the delay after onset of chest pain because the level of troponin may continue to grow up to three hours after the chest pain. This may lead to increase the proportion of false negatives.

From the validation sample, we will estimate its discriminative capacities by the ROC curve and the related AUC. Its goodness-of-fit will be evaluated by a calibration plot of the observed probabilities against the mean predicted probabilities for five subgroups of equal size. The corresponding Hosmer and Lemeshow statistic will be estimated.

Always from the validation sample, we will compute the in-hospital HEART score at 0h, the related ROC curve and AUC, and its difference with the pre-hospital predictive model.

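### Section 18 chooses the hs-cTnI thresholds and reports their performance on the same patients without an optimism correction, so apparent sensitivity and Youden J are too high on average

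*SAP*

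**What the plan says.** Section 7 sets the primary objective: "The primary objective is to determine the thresholds of the pre-hospital capillary and venous hs-cTnI that maximizes the Youden J index". It defines sensitivity and specificity at that threshold, with NSTEMI at discharge as the event. Section 18 restates the objective for the capillary method ("The primary objective is to determine the pre-hospital capillary hs-cTnI threshold that maximizes the Youden index") and puts the venous results on the same figure. It adds a second criterion: "The Euclidean distance (also called the upper-left index) will also be estimated". For the resulting thresholds, "The related effectives (true positives and negatives, false positives and negatives) will be reported", together with accuracy.

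Three other places bear on the point:

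- Section 13 on intervals: "The 95%CI will be estimated by non-parametric bootstrap". It does not say whether the threshold is chosen again in each resample, and it mentions no bias correction.
- Section 19: "The cohort will be divided into two parts: two thirds for learning and one third for validation". Sections 19 and 20 use this split only for the predictive tool.
- Section 7 extends the comparison to a second outcome, "considering the Major Adverse Cardiac Events (MACE) occurrence at 30 days (ROC curves, AUCs, and Youden J index". The MACE paragraph of section 18 lists only ROC curves, AUCs and their differences.

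**The concern.** A threshold chosen because it gives the highest J in this cohort has partly been chosen for its luck in this cohort. Its counts then describe the cohort correctly, but they overstate what the same threshold will do in new patients. The SAP guards against this for the secondary predictive tool by holding out a third of the cohort. It gives no such protection to the primary threshold.

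Sensitivity is the quantity on which section 10 sizes the study, with a target of plus or minus 5 points. For a marker studied partly for rule-out, an overstated sensitivity means an understated share of missed NSTEMI. The intervals are also left open: two analysts could follow section 13 and produce different intervals for the primary result, depending on whether they re-select the threshold and which quantity they think they are estimating.

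**Working it through.** **The plan's own figure.** Section 10 states a 95% sensitivity, a half-width of 5 points and a 10% prevalence.

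- Cases: 1.96² × 0.95 × 0.05 / 0.05² = 72.99, so 73.
- Patients analysed: 73 / 0.10 = 730, so non-cases are 730 − 73 = 657.
- The stated 800 inclusions are close to 730 × 1.10 = 803 and 730 / 0.90 = 811.1 (812 rounded up).

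The arithmetic reproduces.

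**Direction.** Write J(c) for the true index at cut-off c, Ĵ(c) for the cohort estimate and ĉ for the cut-off that maximises Ĵ. Then E[Ĵ(ĉ)] ≥ max J(c) ≥ J(ĉ): apparent J is biased upward whatever the marker distribution.

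The bias falls mainly on sensitivity because the cases are few. At equal proportions the sampling variance of sensitivity is 657 / 73 = 9 times that of specificity. At 82%, for example, the standard errors are √(0.82 × 0.18 / 73) = 4.5 points and √(0.82 × 0.18 / 657) = 1.5 points.

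**Size.** The SAP gives no AUC or marker distribution, so these are assumptions: continuous normal markers with equal SD, 73 cases and 657 non-cases. Under this model the true sensitivity at the Youden point is Φ(Φ⁻¹(AUC)/√2). At AUC 0.99 this is Φ(2.326/1.414) = Φ(1.645) = 95%, the value section 10 expects.

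Each scenario used 2,000 simulated cohorts with 400 bootstrap resamples within outcome status, re-selecting the threshold each time. Optimism is apparent minus true performance at the selected threshold. The correction subtracts the mean of (resample performance − performance of the resample's threshold in the original sample). Entries are points, except true sensitivity (%).

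| AUC | True sensitivity | Optimism, sensitivity | Optimism, J | Mean correction, sensitivity | Remaining, sensitivity | Remaining, J |
|---|---|---|---|---|---|---|
| 0.80 | 72 | +4.2 | +4.6 | 3.0 | +1.2 | +1.3 |
| 0.85 | 77 | +3.8 | +4.1 | 2.8 | +1.0 | +1.1 |
| 0.90 | 82 | +3.5 | +3.8 | 2.4 | +1.1 | +1.1 |
| 0.95 | 88 | +3.1 | +3.3 | 2.1 | +1.0 | +1.0 |
| 0.99 | 95 | +2.2 | +2.4 | 1.4 | +0.8 | +0.8 |

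Monte Carlo error is about 0.1 point. Specificity is overstated by at most 0.4 and accuracy by at most 0.8. Apparent sensitivity exceeds the truth in about 80% of cohorts. The share of sensitivity bias left after correction runs from 1.0/3.8 = 26% to 0.8/2.2 = 36%.

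**Variations.**

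- Upper-left threshold, over the same AUCs: sensitivity +3.1 down to +1.9, J +3.3 down to +2.0; at most +0.9 after correction.
- Case SD 1.5 to 3 times that of non-cases, AUC 0.80 to 0.99: sensitivity +1.6 to +3.9.
- Log-normal markers give the same result as normal ones, because the selection uses ranks only.
- Coarse recording in steps of 0.5 SD (an assumption; the SAP gives no assay resolution): sensitivity about +1.8, +1.3 and +1.0 at AUC 0.80, 0.90 and 0.99. Milder rounding (log-normal values, whole units, floor at 2) gives +3.1 at AUC 0.80 down to +1.9 at 0.99.
- MACE Youden threshold, over the same AUCs: sensitivity +3.3 down to +1.6 at an assumed 15% MACE rate (110 of 730), and +2.6 down to +1.3 at 20% (146 of 730).

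**Intervals.** Coverage of a nominal 95% percentile bootstrap that re-selects the threshold, at AUC 0.80/0.85/0.90/0.95/0.99 (Monte Carlo error about 1 point):

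| Target | Sensitivity, % | J, % |
|---|---|---|
| Performance at the reported threshold | 88/87/86/81/70 | 73/75/75/73/65 |
| Population Youden point | 95/96/93/93/86 | 79/81/81/79/74 |

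At 95% sensitivity the mean interval length is 7.6 points.

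**The case against.** The strongest reply is that little hangs on this figure. The stated aim is to determine a threshold, section 18 is headed as a description, and the counts it reports will be true of the cohort. Where performance is meant to support use, sections 19 and 20 rely on held-out patients. The capillary/venous comparison rests on AUC, which involves no threshold selection. All of this stands and limits the consequences. It does not make the sensitivity at a published threshold an unbiased figure.

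The size is also open to challenge, and that stands too. The 4-point end belongs to AUC 0.80 and a true sensitivity of 72%, which the SAP does not plan for. At its own 95% the model gives about 2 points, and coarse recording reduces the bias further. The direction is secure; the size is conditional.

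On intervals, a reader might infer that the planned bootstrap is simply invalid. The SAP does not support that: it names no target, and for the population Youden point the sensitivity interval is near nominal at AUC 0.80 to 0.95 in the equal-SD model. The case for naming the target is sound, but choosing it is the sponsor's decision. J under-covers for either target.

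A reader might also infer that the sample size is wrong because maximising J does not aim at 95% sensitivity. Section 10 states its assumption openly ("For the primary objective, we expect a sensitivity of 95" per cent), its arithmetic is right, and the 10-point length is met at that sensitivity.

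Finally, the correction is incomplete. That is so, but it also lowers the root mean squared error of sensitivity, from 6.4 to 5.3 points at AUC 0.80 and from 3.5 to 2.9 at AUC 0.99.

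**Conclusion.** The concern holds in a limited form. Followed as written, section 18 overstates sensitivity and J at the selected thresholds on average. With 73 cases, 657 non-cases and continuous equal-SD normal markers, the overstatement is about 2 points at the expected 95% sensitivity (AUC about 0.99). At AUC 0.80 it is about 4 points for sensitivity and 4 to 5 for J. It is about 1 to 2 points if the marker is coarsely recorded. These sizes rest on assumptions outside the SAP; the upward direction held in every model tried.

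It would be going too far to say that the choice between capillary and venous sampling, or the rule-out and rule-in results, are compromised. The first comparison uses AUC, the second uses the validation sample, and no later SAP decision uses the Youden-point sensitivity. The change is worth making because it concerns the primary result and costs almost nothing.

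**What to change.** In section 18, with a cross-reference in section 13:

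1. State that each bootstrap resample re-selects the threshold and that this threshold is then applied to the original sample. Optimism is resample performance minus original-sample performance, averaged over resamples.
2. Report optimism-corrected sensitivity and J (apparent minus mean optimism) beside the apparent values, and label each. Do this for capillary and venous, for the Youden and upper-left thresholds, and for the MACE Youden index named in section 7.
3. State that the bootstrap confidence intervals re-select the threshold, and whether they target performance at the reported threshold or at the population Youden point. Note that coverage differs between the two and that a plain percentile interval under-covers J for both.

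Section 10 needs no change.

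Cost: a few sentences of SAP text, a small extension of a bootstrap already planned, slightly more computation and no extra patients. In the continuous normal model the headline Youden sensitivity falls by about 1.4 to 3.0 points on average, and roughly a third of the bias remains, so the corrected figure should not be presented as bias-free.

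### Capillary–venous agreement is judged by a plain-difference plot and one ICC of unstated form and scale, without comparing how the two methods classify the same patient, so a proportional bias at low values could go unnoticed

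*SAP*

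**What the plan says.** SAP section 7 lists, among the secondary objectives, finding the more relevant of the two sampling methods by two routes: "reporting the concordance between the pre-hospital hs-cTnI measured by the capillary and venous methods" and "comparing the related AUCs for discriminating patients with NSTEMI". A sentence further on in that section ties the choice of method for later analyses to discriminative performance, with capillary as the default if the two are equivalent.

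Section 18 sets out the agreement analysis. The summary statistic is described as follows: "The intra-class correlation coefficient (ICC) will additionally provide a single measure of the agreement between the capillary- and venous-based methods". Two plots go with it: venous against capillary values, and "a Bland–Altman plot with the difference between the two measurements (y-axis) against the average of the two measurements (x-axis"). The axes of the second plot are therefore the plain difference and the plain mean. No log, ratio or percentage difference is named. The ICC has no stated form (consistency or absolute agreement) and no stated scale.

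Section 18 then says: "Depending on the results at this stage, the rest of the analyses will be performed according to the venous or the capillary method". True and false positives and negatives are to be reported at the thresholds. These are counts of each method against the diagnosis, not a table of one method against the other in the same patients. The only remedy concerning scale in the SAP, B-splines in section 22, belongs to the predictive model.

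**The concern.** A marker of myocardial injury, measured in a cohort where most patients have no infarction, can be expected to be strongly right-skewed, with measurement error that grows with level. This is an assumption, since the SAP describes no distribution. Under it, the two planned agreement summaries serve poorly in the low range, in different ways.

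- An ICC on raw values compares error with the spread between patients. When that spread is very wide, the ICC is close to 1 almost regardless of what happens at low values.
- Limits of agreement computed on raw differences over the whole range reflect the error at high values. They are too wide to describe low ones.

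The AUC comparison does not fill the gap. It depends on ranks only, so a capillary reading that is proportionally too low leaves it practically unchanged. Detecting such a bias is the task of the agreement analysis. What is at stake is whether a threshold found with one method can be applied to readings from the other, and section 18 makes a threshold the primary result: "The primary objective is to determine the pre-hospital capillary hs-cTnI threshold that maximizes the Youden index".

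**Working it through.** **The plan's own figures.** The SAP gives no figure for the agreement analysis. Only the cohort size and prevalence are taken from section 10: "Assuming a NSTEMI prevalence of 10%, 730 patients must be analyzed to achieve this precision". They reproduce: 1.96² × 0.95 × 0.05 / 0.05² = 72.99, so 73 patients with NSTEMI, and 73 / 0.10 = 730.

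**Assumed inputs, not in the SAP.** Lognormal values; without NSTEMI, median 5 ng/L and log-SD 0.9; with NSTEMI, median 15 to 60 ng/L and log-SD 0.8 to 1.5 (the wide case is median 60, log-SD 1.5); an illustrative cut-off of 10 ng/L. The bias scenario has capillary readings 30% too low below 20 ng/L and unbiased above.

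**Step 1: AUC.** Multiplying by 0.7 below 20 ng/L and by 1 from 20 ng/L upward is a strictly increasing map. Ranks are kept, so without random error the two AUCs are identical. With random error, in simulation, they stay within 0.001 of each other.

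**Step 2: discordant classification, by hand without random error.** Patients with a venous value from 10 to 10/0.7 = 14.3 ng/L read below 10 ng/L on the capillary sample.

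- Without NSTEMI: Φ(ln(14.3/5)/0.9) − Φ(ln(10/5)/0.9) = Φ(1.17) − Φ(0.77) ≈ 0.099.
- With NSTEMI, wide case: Φ(−0.96) − Φ(−1.19) ≈ 0.053. Total: 0.9 × 0.099 + 0.1 × 0.053 ≈ 9.4%.
- With NSTEMI, median 15 and log-SD 0.8: Φ(−0.06) − Φ(−0.51) ≈ 0.170. Total: 0.9 × 0.099 + 0.1 × 0.170 ≈ 10.6%.

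Simulation with N = 730 and random error gives 9 to 11%.

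**Step 3: raw ICC.** The two-way absolute-agreement form is (MSR − MSE) / (MSR + MSE + 2(MSC − MSE)/n), with mean squares for patients (R), methods (C) and error (E). In the bias scenario it is 0.96 to 0.99.

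**Step 4: what a ratio scale shows.** In the wide case the share of patients below 20 ng/L is 0.9 × Φ(ln(4)/0.9) + 0.1 × Φ(ln(1/3)/1.5) = 0.9 × 0.938 + 0.1 × 0.232 ≈ 0.87. The geometric mean capillary/venous ratio is then 0.7^0.87 ≈ 0.73, and simulation agrees. A ratio-scale Bland–Altman analysis would report this bias directly.

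**Step 5: raw limits of agreement, wide case.** Over the whole range they are about ±29 ng/L. Among patients with a mean below 20 ng/L they are about ±3 ng/L (10% error plus additive SD 1 ng/L, here with non-NSTEMI median 4 ng/L and log-SD 0.8) to ±6 ng/L (30% error below and 10% above 20 ng/L). A 30% bias at 5 ng/L is 0.3 × 5 = 1.5 ng/L, which is invisible against ±29.

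**Step 6: would a log-scale ICC be enough?** No. In the wide case it is about 0.87 to 0.96 across a 30% low-range bias and 30 to 50% low-range imprecision. Most readers would call that good or excellent.

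**The case against.** The strongest reply is that section 7 ties the choice of method to discriminative performance, and the AUC is unaffected by scale. The ICC is described as an additional summary, with no cut-off and no test. This stands: a flattering ICC is unlikely to change which method is carried forward.

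A second reply is that each method receives its own Youden threshold, which would absorb a proportional bias. This also stands as far as it goes. The bias matters when a threshold from one method is applied to readings from the other, and nothing planned measures that.

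A third reply is that the plots show every patient and that the counts against the diagnosis are reported. The plots help, although on raw axes low values crowd near the origin. The counts are not paired between methods.

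A reader might also infer more than the SAP supports:

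- That a handful of extreme values creates the high ICC. Under these assumptions the top 1% of patients do carry most of the variance in the wide case, but removing them lowers the raw ICC only from 0.991 to 0.985. The cause is the wide spread between patients generally.
- That raw limits hide low-range error. Limits over the whole range overstate it.
- That an ICC restricted to values below 20 ng/L reveals how poor agreement is. Part of any fall comes from restricting the range: with the same 20% error throughout, the ICC drops from 0.97 to 0.90 for that reason alone.
- That the SAP prescribes a raw ICC. It is silent, and raw is only the default reading.

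**Conclusion.** The point holds as a modest improvement to the concordance objective. Section 18 fixes plain-difference axes, leaves the ICC undefined and omits any paired classification. Under the stated assumptions, a 30% low-range capillary bias would coexist with a raw ICC of 0.96 to 0.99 and AUCs equal to within 0.001, while about 9 to 11% of patients fell on different sides of a shared 10 ng/L cut-off.

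All of these sizes rest on assumed distributions, an assumed bias and an illustrative cut-off. The SAP gives none of them, and its background section describes the device as comparable to central laboratory testing. The documents therefore do not support the inference that the two methods actually disagree at low values, or that the planned analysis would select the wrong one. What they support is that the planned summaries could not be relied on to show such a bias if it existed.

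**What to change.** Amend section 18 as follows.

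1. Draw the Bland–Altman plot on log-transformed hs-cTnI and report the bias and limits of agreement back-transformed as capillary/venous ratios. State how readings at zero or below the detection limit are handled before logs are taken.
2. Cross-classify patients by the two methods at the Youden threshold and report the discordant share with a 95% CI. Apply the same threshold to both readings, since this tests whether it transfers; a second table with each method at its own threshold can be added. The bootstrap already planned in section 13 can supply the interval, resampling patients so that pairs stay together and re-estimating the threshold each time.
3. Define the ICC as absolute agreement on the log scale, with a 95% CI, and label it supplementary because it too stays high in the scenarios above.

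The raw scatter and difference plots may remain as a supplement. The cost is a change of wording and a little extra analysis of the same data, with no additional patients or measurements.

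### The capillary method is carried forward in case of equivalence, but the SAP defines no equivalence criterion and its only test is a two-sided test for a difference

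*SAP*

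**What the plan says.** Section 7 of the SAP makes the two-method comparison a gate: "the rest of the analyses will be performed according to the venous or the capillary method, depending on their discriminative performances". Sections 7 and 18 both name the tie-break, which section 18 words as "In case of an equivalence, we will choose the capillary method because of its feasibility in a real-life setting".

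Four results are available at that gate, all in section 18:
- **AUC for NSTEMI.** "The difference between the two curves will be estimated and the corresponding bilateral test to evaluate the significance will be performed from the 95%CI". Section 13 sets the level at 5%, with "two-sided alternative hypotheses and two-sided 95% confidence intervals", and adds: "The 95%CI will be estimated by non-parametric bootstrap".
- **ICC.** "The intra-class correlation coefficient (ICC) will additionally provide a single measure of the agreement between the capillary- and venous-based methods". No acceptable value is given.
- **Scatter and Bland–Altman plots.** No limits of acceptable disagreement are given.
- **AUC for MACE at 30 days.** "The related AUCs and differences will be reported". No decision threshold is given, and the SAP does not say whether NSTEMI or MACE prevails if they disagree.

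No section of the SAP defines equivalence.

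**The concern.** Choosing capillary as equivalent requires evidence that it is not worse than venous by more than a tolerable amount. The plan supplies a test of the opposite kind, one that looks for evidence of a difference. When such a test is non-significant, the data may show that the methods perform alike, or may simply be too few to tell. The word equivalence is left to be filled in once the results are known, and the reading closest to hand is that the 95% CI of the AUC difference includes zero.

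The choice settles which hs-cTnI value enters the LASSO model and the comparison with the HEART score (section 19), and the rule-out and rule-in estimates (section 20). Selecting the better method is also a secondary objective in its own right (section 7).

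**Working it through.** **1. The plan's own figures.** Section 10 assumes a sensitivity of 95%, a half-width of 5% and a prevalence of 10%.
- n = 1.96² × 0.95 × 0.05 / 0.05² = 72.99, so 73 events.
- 73 / 0.10 = 730 analysed, so 730 − 73 = 657 non-events.
- Allowing for 10% unusable data: 730 / 0.9 = 811, or 730 × 1.1 = 803. The stated 800 is close to both.

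The sample size was set by the precision of one sensitivity. It does not address the capillary–venous comparison.

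**2. Assumptions.** The SAP gives no AUC, no correlation between methods and no margin. I took a venous AUC of 0.85, marker correlations of 0.7 to 0.95, and true capillary losses of 0, 0.03 and 0.05.

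**3. Simulation.** Binormal markers, 73 events and 657 non-events, paired DeLong standard error, 1,500 trials per setting (Monte Carlo error at most √(0.25/1,500) = 1.3 percentage points). Non-significant means that the 95% CI of the AUC difference includes zero.

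| Marker correlation | 0.7 | 0.8 | 0.9 | 0.95 |
|---|---|---|---|---|
| True loss 0.03, non-significant | 69% | 57% | 31% | 7% |
| True loss 0.05, non-significant | 35% | 18% | 3% | 0% |

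**4. Cross-check by formula.** The Hanley–McNeil variance is V = [A(1−A) + (n₁−1)(Q₁−A²) + (n₀−1)(Q₂−A²)] / (n₁n₀), with Q₁ = A/(2−A) and Q₂ = 2A²/(1+A).
- At A = 0.85: Q₁ = 0.7391, Q₂ = 0.7811, A² = 0.7225. V = (0.1275 + 72 × 0.0166 + 656 × 0.0586) / 47,961 = 0.00083.
- With equal AUCs, the SE of the paired difference is √[2V(1−r)], where r is the correlation between the two AUC estimates. This gives 0.022, 0.018 and 0.013 at r = 0.7, 0.8 and 0.9, and 95% half-widths of 0.044, 0.036 and 0.025.
- Using the SE that applies when the AUCs differ, a loss of 0.03 is non-significant in 75%, 65% and 39% of trials, and a loss of 0.05 in 44%, 27% and 5%.

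These rates are somewhat higher than in step 3. The variance formula differs, and r here refers to the AUC estimates, whose correlation is lower than that of the markers. The direction is the same.

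**5. A margin rule on the same interval.** Capillary passes if the lower 95% limit of AUC(capillary) − AUC(venous) lies above minus the margin. For an illustrative margin of 0.05, in the simulation:

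| Marker correlation | 0.7 | 0.8 | 0.9 | 0.95 |
|---|---|---|---|---|
| No true difference, passes | 75% | 88% | 99% | 100% |

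A true loss equal to the margin passes in only about 3–4% of trials. A true loss of 0.03, which lies inside that margin, passes in 40% at correlation 0.9 and 58% at 0.95. The non-significance reading would accept it in 31% and 7%. The margin rule therefore caps the error at the stated margin, but its value depends on the margin being the right one.

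**The case against.** A reader might infer that the SAP equates a non-significant difference with equivalence. It does not say so. Section 7 refers to discriminative performances and section 18 to the results at that stage, which include the ICC, the plots and the MACE AUCs. The phrase could be meant as a plain tie-break. This part of the objection stands: what is shown is an undefined rule, not a wrong one written down. It does not remove the problem, because the ICC and plots have no acceptance limits and no other stated test could carry the conclusion.

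A reader might also infer that a clearly worse method will be carried forward. That depends on a correlation the SAP does not give. Both samples come from the same patient, and section 5 describes one device that accepts either, so a high correlation is plausible. At 0.9, a loss of 0.05 would be missed in only about 3% of trials.

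The consequences are also bounded. Section 7 asks for thresholds under both methods, so the primary result does not hinge on the choice. The planned CI of the AUC difference shows a reader how large a loss is excluded. The tool is assessed in a validation third using the method actually chosen, so a weaker predictor should lower its reported performance, not inflate it. These points limit the severity. They do not supply the missing criterion.

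**Conclusion.** The point holds as a badly fixed decision rule that should be repaired, though it does not threaten the primary objective. Following the plan can yield a statement of equivalence that its analysis cannot support. The size of the risk depends on the assumed AUC of 0.85 and on the marker correlation. It is substantial at 0.7 to 0.8, where a loss of 0.03 goes undetected in more than half of trials and a loss of 0.05 in about one in six to one in three. It is small at 0.95. The documents do not support saying that non-significance is the SAP's stated criterion, or that an inferior method is bound to be selected.

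**What to change.** In section 18, before the data are analysed:
- State a margin for the AUC difference and justify it on clinical grounds.
- Carry capillary forward as equivalent only if the lower limit of the 95% bootstrap CI of AUC(capillary) − AUC(venous) for NSTEMI lies above minus that margin. NSTEMI is the natural choice because it is the primary event and the outcome of the later model.
- Otherwise use venous, or state that capillary is chosen for feasibility with no claim of equivalence.
- Say that the ICC, the plots and the MACE comparison are supportive, or give them limits if they are to count in the choice.

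A margin of 0.05 should not be adopted merely because this sample can attain it. Its power is only about 75% at correlation 0.7, and at 0.9 to 0.95 it accepts a true loss of 0.03 in 40% to 58% of trials.

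The cost is SAP wording: the bootstrap interval is already planned and no further data are needed. The downside is that a margin has to be defended, and capillary may fail it if the two methods correlate poorly.
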